12.2.2. Adverse Events of Special Interest (AESIs)

The following AESIs have been identified as requiring mitigation steps and monitoring to minimize the risk for the occurrence of these events. All potential and identified AESIs must also be discussed with the Medical Monitor and reported following the procedures for reporting SAEs (Section 12.4).

12.2.2.1. T-Cell Lymphoblastic Lymphoma/T-Cell Acute Lymphoblastic Leukemia

Lymphoblastic lymphomas are considered thymus derived malignancies that have not yet completed T-cell maturations. Approximately 90% of lymphoblastic lymphomas are the T-cell phenotype and typically occur in young adults and adolescents, accounting for 29% of pediatric and 2% of adult non-Hodgkin lymphoma with a median age at diagnosis of 25 years (Lones, 2007; Lai, 2013; Cortelazzo, 2017). T-LBL is morphologically and immunophenotypically indistinct from T-ALL, with both diseases arising from precursor lymphoid cells of the T-cell lineage (Portell, 2012; Patel, 2014). Despite the similarities of the two diseases, significant yet unknown characteristics lead to differences in clinical presentations (Burkhardt, 2009). Initial clinical manifestation of both adult and pediatric T-LBL includes a mediastinal mass or lymphadenopathy with <25% bone marrow blasts. Adult T-LBL subjects tend to have less thymic disease and greater lymph node disease and bone marrow involvement (Baleydier, 2008; Campo, 2011; Swerdlow, 2017). In contrast, T-ALL cases predominantly present with bone marrow and peripheral blood disease, and >25% bone marrow blasts (Campo, 2011; Swerdlow, 2017).

CCI

This event was reported to regulatory authorities as a 7-day suspected unexpected serious adverse reaction (SUSAR) on 13 April 2018 (PPD).

Following this report, Epizyme conducted a comprehensive evaluation, including:

- Review of literature and available preclinical/clinical data to better understand event of T-LBL.
- Review of the literature and available preclinical/clinical data to better understand the risk of MDS/AML and myeloid malignancies, and other solid tumor malignancies.
- Assessment of safety, pharmacokinetics at various doses tested, benefit-risk across tumor types in adults and children.
- Consultation with well recognized external experts in T-cell malignancies and pediatric/adult oncology.

Based on this evaluation, we continue to believe that tazemetostat is a clinically active drug and has the potential to benefit both adult and pediatric subjects across different tumor types where there are unmet medical needs. We also conclude that the risk assessment identifies a possible direct association between tazemetostat and T-LBL/T-ALL. Epizyme considers the risk for T-LBL/T-ALL in tazemetostat clinical trials to be largely concentrated in pediatric subjects based on 1) higher area under the concentration-time curve from zero time to 24 hours (AUC₀₋₂₄) exposures in pediatric subjects 2) increases over time in age-related thymic involution, and 3) the known epidemiology / pathophysiology of T-LBL/ALL. The risk of T-LBL/T-ALL in adults is not known, however the incidence of treatment-related T-LBL/T-ALL in adults. Refer to the tazemetostat IB for further details.

12.2.2.2. Myelodysplastic Syndrome/Acute Myeloid Leukemia/Myeloproliferative Neoplasm

Five myeloid AESI in the adult population have been reported in the adult population. The three AML cases were reported in one subject each with rhabdoid sarcoma and FL and DLBCL. The DLBCL subject experienced MDS which then transformed into AML. Two cases of MDS were reported in one subject each with FL and DLBCL.

In the event of suspicion of these malignancies or related concerns, please contact the Medical Monitor for evaluation and consideration of dose adjustments. Heightened surveillance will be conducted to monitor and identify early signs and symptoms (per local practice/standard of care) of any MDS/AML and other myeloid malignancies like MPN. For any MDS/AML or other myeloid malignancies like MPN, tazemetostat will be discontinued.

12.2.3. Disease-Related Events

Events that meet the criteria for serious but are thought to be due to the underlying malignancy or associated with progression of disease under study should be reported as SAE if untoward.

Note: Disease progression per se should not be reported as an SAE term in and of itself.

All SAEs that occur after any subject has been enrolled, before treatment, during treatment, or within 30 days following the cessation of treatment, whether or not they are related to the study, must be reported to Epizyme, Inc.

12.2.4. Other Risks

Refer to the respective package inserts or IB and established treatment guidelines and dose modified according to approved product labeling or IB for additional risks.

12.2.4.1. Identified Risks

12.2.4.1.1. Associated with Tazemetostat

- Events of thrombocytopenia, neutropenia, or anemia (Grade 3 or Grade 4).
- AEs associated with treatment overdose, misuse, abuse, or medication error; and any treatment-emergent significant laboratory abnormality.

These other identified or potential risks are to be captured using the SAE procedures but are to be considered as SAEs only if they met one of the above criteria. All other identified or potential risks are to be reported on the eCRF whether or not they meet the criteria for an SAE.

12.2.4.1.2. Associated with Rituximab

Other identified risks for rituximab include:

[figure not shown]
- Tumor lysis syndrome
- Infections
- Cardiac adverse reactions
- Renal toxicity

- Bowel obstruction and perforation
- Immunizations: Live virus vaccinations prior to or during rituximab treatment is not recommended
- Embryo-fetal toxicity: Can cause neonatal harm

For rituximab, refer to the current manufacturer's prescribing information.

12.2.5. Special Situations: Overdose, Misuse, Abuse and Medication Error

Definitions, reporting, and management of overdose, misuse, abuse, and medication errors are presented below and refer to tazemetostat.

- Overdose: An overdose is defined, regardless of any associated AEs or sequelae, as:
 - On a per dose basis, any amount of the orally administered drug(s) that is over the protocol-specified dose assigned to a given subject.
 - On a schedule or frequency basis, anything taken more frequently than the protocol-required schedule or frequency.
- **Misuse**: Intentional and inappropriate use of study drug not in accordance with the protocol.
- **Abuse:** Sporadic or persistent intentional excessive use of study drug accompanied by harmful physical or psychological effects.
- **Medication error:** Any unintentional event that causes or leads to inappropriate study drug use or subject harm while the study drug is in the control of site personnel or the subject.

These occurrences must be reported on the dosing administration eCRF. Adverse events associated with these occurrences are to be captured on the AE eCRF.

All instances of special situations are to be reported using the paper special situations form regardless of presence or absence of an associated AE. Refer to Section 12.4.3 for detailed instructions on how to handle the reporting of special situations.

In the event of a special situation, the Investigator should immediately contact the Medical Monitor or their designee and closely monitor the subject for AEs and laboratory abnormalities.

12.3. Relationship to Study Drug

A qualified Investigator must make the determination of relationship to tazemetostat for each AE. The Investigator should decide whether, in his or her medical judgment there is a reasonable possibility that the event may have been caused bytazemetostat.

Items to be considered when assessing the relationship of an AE to the study drug are:

- Temporal relationship of the onset of the event to the initiation of the study drug
- The course of the event, considering especially the effect of discontinuation of study drug or reintroduction of study drug, as applicable
- Whether the event is known to be associated with the study drug or with other similar treatments
- The presence of risk factors in the study subject known to increase the occurrence of the event
- The presence of non-study drug-related factors which are known to be associated with the occurrence of the event.

Classification of Causality

- Not Related: A causal relationship between the study drug and the AE is not a reasonable possibility.
- Related: A causal relationship between the study drug and the AE is a reasonable
 possibility. The Investigator must further qualify the degree of certainty as "possible"
 or "probable."

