Safety will be assessed through summaries of AEs, laboratory evaluations, vital signs, and physical examinations. Safety analyses will be based on all enrolled subjects who receive at least 1 dose or partial dose of study drugs (safety population). Drug exposure will be summarized by descriptive statistics. Severity of all AEs is to be evaluated by the Investigator based on the CTCAE, version 5.0 and will be coded to preferred term, higher level term, and system organ class using the Medical Dictionary for Regulatory Activities (MedDRA; version 23.1). The number and percentage of subjects with AEs will be presented by MedDRA system organ class and preferred term, relationship to study treatment, and severity. Descriptive statistics will be used rather than inferential statistics. Laboratory values also will be classified by toxicity grade based on the NCI's CTCAE, version 5.0. Laboratory shift tables of the baseline results to each of the subsequent visits will be produced.

Statistical Methods:

Primary Efficacy Endpoint - All Phase 2 Cohorts

• ORR: ORR is defined as the proportion of the FAS subjects with WT EZH2 status achieving a CR or PR according to the 2014 Lugano Classification (Appendix 3) as assessed by Investigator and blinded IRC at the following time points: Cycle 3, Cycle 6, Cycle 12, Cycle 18, and Cycle 24. Subjects with a best response of unknown/non-evaluable response will be treated as non-responders, (i.e., they will be

Name of Investigational Product: Tazemetostat (EPZ-6438)

Name of Active Ingredient: Tazemetostat

included in the denominator when calculating the percentage). ORR will be presented with corresponding 2-sided 95% CIs. This analysis will be performed on a subset of the FAS that includes all subjects with WT EZH2 status.

Secondary Efficacy Endpoints:

- **PFS:** The PFS, defined as the time from the first dose of study drug to the earliest date of disease progression per the 2014 Lugano Classification (Appendix 3) or death from any cause, whichever occurs first, will be assessed by IRC. PFS will be estimated using Kaplan-Meier method and presented with corresponding 2-sided 95% CIs. PFS will be analyzed using the FAS.

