6.1.2. Secondary Objectives

- To evaluate the safety of the combination of tazemetostat and rituximab by assessing the incidence of adverse events/serious adverse events, change of vital signs, lab results, and physical exam findings from baseline
- To estimate median progression-free survival (PFS) of tazemetostat in combination with rituximab at 2 years in subjects with R/R FL and WT EZH2 status, and in the pooled group regardless of mutation status.
- To explore the response rate in a subset of subjects with MT EZH2.
- Evaluation of efficacy outcomes in rituximab refractory subjects

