7.4.2. Dose Adjustment for Rituximab

The dose of rituximab should not be reduced. Administration of rituximab may be interrupted and modified according to the clinical practice of the Investigator's institution (eg, dose splitting or dose banding), and in line with the approved prescribing information including administration, warnings, precautions, contraindications, and adverse reactions, as applicable. In case a dose of rituximab is missed during Cycle 1 because of toxicity, it will not be rescheduled. In case of delay in the start of the next cycle (Cycles 3 through 6) due to toxicity, rituximab administration will be postponed until AE has resolved, at which point the next cycle is started. If rituximab is discontinued due to toxicity, tazemetostat should be continued as per protocol and the subject should continue in the study.

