9.2.5. Prohibited Concomitant Therapies and Drugs

Subjects must not receive other antitumor therapies while on study. Prohibited antitumor medications during this study are any other investigational or unapproved drugs, and other anticancer therapies unless otherwise stated. If a subject receives any prohibited antitumor medications, this will be judged as evidence of disease progression, and study drug will be discontinued. In this case, the subject should complete all off-treatment assessments and be followed for survival in the Survival Follow-up period.

Known strong CYP3A inhibitors and strong or moderate CYP3A inducers (including St. John's wort) are prohibited within 14 days prior to the first dose of study drug (tazemetostat) and for the duration of the study. Coadministration of tazemetostat with a strong or moderate CYP3A inhibitor increases tazemetostat plasma concentrations, which may increase the frequency or severity of adverse reactions.

Coadministration of tazemetostat with a strong or moderate CYP3A inducer may decrease tazemetostat plasma concentrations, which may decrease the efficacy of tazemetostat. Because there is a potential for interaction of tazemetostat with other concomitantly administered drugs through the cytochrome P450 system, all over-the-counter medications, and alternative therapies, in addition to prescribed medications, must be recorded in the eCRF. The Investigator should be alerted if the subject is taking any agent known to affect or with the potential to affect selected CYP450 isoenzymes.

Medications that are strong CYP3A inhibitors and strong or moderate CYP3A inducers include, but are not limited to, those listed in Table 4 (refer to product information and the source websites in Table 4 for the most up-to-date information).

Table 4: Examples of Strong and Moderate Clinical CYP3A Inhibitors and Inducers and Clinical CYP3A Sensitive Substrates for P450-Mediated Metabolisms

Strong Inhibitors	Moderate Inhibitors	Strong Inducers	Moderate Inducers	Sensitive Substrates
boceprevir	aprepitant	apalutamide	bosentan	alfentanil
clarithromycin ^a	ciprofloxacin	carbamazepine	efavirenz	avanafil
cobicistata	conivaptan ^d	enzalutamide ^f	etravirine	budesonide
danoprevir and	crizotinib	mitotane	phenobarbital	buspirone
ritonavir ^b	cyclosporine	phenytoin	primidone	conivaptan
elvitegravir and	diltiazeme	rifampin		darifenacin
ritonavir ^b	dronedaronea	St. John's wortg		darunavir ^h
grapefruit juice ^c	erythromycin			dasatinib

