10. STUDY DRUG MATERIALS AND MANAGEMENT

10.1. Study Drug

Rituximab in combination with tazemetostat is under investigation as a treatment for subjects with R/R FL.

A description of the study drugs is provided in Table 6.

Table 6: Study Drugs

Product name	Study Drug (Tazemetostat)	Rituximab	Rituximab
Dosage form:	tablet	solution	solution
Unit dose:	200 mg	100 mg/10 mL or 500 mg/50 mL	1,400 mg/23,400 Units (1,400 mg rituximab and 23,400 Units hyaluronidase human) per 11.7 mL (120 mg/2,000 Units per mL)
Route of administration:	oral	intravenous	subcutaneous
Physical description:	red, round, and biconvex film-coated tablets packaged in white high-density polyethylene bottle with a child resistant, tamper-evident polypropylene screw cap	Refer to current manufacturer's prescribing information	Refer to current manufacturer's prescribing information
Manufacturer:	Manufactured for Epizyme by Patheon	Refer to current manufacturer's prescribing information	Refer to current manufacturer's prescribing information

Biosimilar formulations for rituximab will be allowed during the study.

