14.7. Criteria for Early Stopping Due to Unacceptable Rates of Adverse Events

Criteria will be in place for halting enrollment and treatment due to safety findings:

- Any fatality that is at least possibly related to treatment calls for immediately stopping accrual and treatment. If attribution is in doubt, the study should be halted until attribution is definitively determined and a decision is made by the study team.
- Two or more observations of a secondary myelodysplastic syndrome or AML or secondary malignancy attributed to tazemetostat will result in stopping accrual and treatment. (Note: observations may not occur during the study period and may occur later, after it is too late to stop accrual.)
- Continuous monitoring with Pocock-like boundaries using the method of Ivanova (Ivanova, 2005) will be utilized for other categories of adverse events, with following rates applied to the continuous stopping rules:
- Combined rate of reportable SAE or SUSAR: 10%
 - Any single category of grade > 3 AE: 50%
 - Grade >3 non-hematologic AE overall: 30%

A table of stopping boundaries for these criteria are provided in Appendix 5. These criteria are independent of the futility analysis for efficacy and will be applied to all subjects that receive any treatment with tazemetostat, regardless of mutation status. See Appendix 2 for details. The stopping rules assume a full accrual of 54 subjects in order to retain statistical properties.

However, if the study stops early due to futility, any bias introduced in the stopping rules due to a change in total accrual should no longer be a concern.

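### Causality is judged for tazemetostat only, while the fatality rule, AE follow-up and the synopsis AE table use relationship to treatment, so rituximab-only events can be left out

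*Protocol*

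**What the plan says.** Protocol Section 12.3 sets the causality assessment: "A qualified Investigator must make the determination of relationship to tazemetostat for each AE". The investigator then decides whether tazemetostat may have caused the event. The answer is Related, qualified as possible or probable, or the alternative: "Not Related: A causal relationship between the study drug and the AE is not a reasonable possibility". Neither the protocol nor the SAP asks for a separate attribution to rituximab.

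Other passages work with a wider idea of treatment:

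- Section 14.7, on fatalities: "Any fatality that is at least possibly related to treatment calls for immediately stopping accrual and treatment". If attribution is in doubt, the study is halted until it is settled. The next rule in 14.7, on secondary malignancies, is limited to events attributed to tazemetostat.
- Section 12.3.2 requires treatment-related AEs to be followed until they resolve, stabilise or are otherwise explained, even after the subject has left the study.
- The synopsis presents AEs by "relationship to study treatment, and severity".
- Section 7.4.2 assumes that rituximab toxicity can be identified: "If rituximab is discontinued due to toxicity, tazemetostat should be continued as per protocol". Section 12.2.4.1.2 lists rituximab's own risks.

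The term study drug is not used uniformly. In Section 10.1 it covers both products ("A description of the study drugs is provided in Table 6", and that table includes intravenous and subcutaneous rituximab). In Section 9.2.5 it means one: "prior to the first dose of study drug (tazemetostat) and for the duration of the study".

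**The concern.** The protocol collects one attribution and uses another. A reader who follows 12.3 literally records an event caused only by rituximab as Not Related. Anyone who later takes that record as the measure of relationship to treatment leaves the event out of the relatedness breakdown, and the duty to follow it to resolution no longer clearly applies. The fatality rule acts on a single death, so one such record could decide whether the rule is recognised as met. Section 14.7 itself separates treatment in one rule from tazemetostat in the next, so the two terms should not be assumed to be interchangeable.

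**Working it through.** **1. How 12.3 classifies an event, by the investigator's opinion of its cause**

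- Tazemetostat alone: Related.
- Tazemetostat and rituximab together: Related, because tazemetostat is a reasonable possibility. Rituximab's share is not recorded.
- Rituximab alone, held with confidence: Not Related. The section also tells the investigator to weigh factors unrelated to the study drug, and if that term means tazemetostat, rituximab is such a factor.
- Uncertain: Related (possible) if tazemetostat is a reasonable possibility. For a death, 14.7 separately calls for a halt while attribution is in doubt.

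The mismatch is therefore confined to the third case.

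**2. Which uses depend on causality**

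- Fatality rule (14.7): yes, relation to treatment.
- Follow-up to resolution (12.3.2): yes, treatment-related.
- Synopsis AE table: yes, relation to study treatment.
- Relationship attribute of the safety endpoint (6.2.2): yes, relation to study drug. This agrees with 12.3 only if study drug means tazemetostat.
- Secondary-malignancy rule (14.7): yes, but it names tazemetostat and so agrees with 12.3.
- The 50% and 30% boundaries for grade >3 events (14.7): no causality condition. Rituximab events count.
- The 10% boundary for reportable SAEs or SUSARs (14.7): only the SUSAR part needs a suspected relation. Reportable is not defined there.
- Safety objective (6.1.2), "To evaluate the safety of the combination of tazemetostat and rituximab by assessing the incidence" of AEs and SAEs: no causality condition.
- SAE reporting to the sponsor during treatment and for 30 days afterwards (12.2.3, 12.4): no causality condition.
- AE listings (SAP 10.1): none is restricted to related events.

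So 12.3 does not match three uses: the fatality rule, follow-up to resolution and the synopsis table. The relationship attribute in 6.2.2 is ambiguous.

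**3. How often the third case could matter for the fatality rule**

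The documents give no rate of death attributed to rituximab alone, so the rate q is an assumption. The chance of at least one such death in n subjects is P = 1 − (1 − q)^n.

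The formula reproduces the protocol's own statement in Section 14.6 for an AE with a true rate of 5% in 54 subjects: 1 − 0.95^54 = 0.937, against the stated 93%.

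With n = 54 (planned evaluable) and n = 5 (treated, SAP 5.2):

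- q = 0.25%: 12.6% and 1.2%
- q = 0.5%: 23.7% and 2.5%
- q = 1%: 41.9% and 4.9%
- q = 2%: 66.4% and 9.6%

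These are the chances that such a death occurs at all. They become chances of a missed halt only if the 12.3 answer alone is used to apply the rule, which the protocol does not say.

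**The case against.** The strongest reply is that 14.7 needs no repair. It already refers to treatment, does not cite the 12.3 assessment, and halts the study when attribution is in doubt. Fatal events are serious, and SAEs during treatment or within 30 days of its end go to the sponsor whether or not they are related, so the sponsor would see such a death. This stands as far as it goes: the gap is an operational risk, not a limit written into the rule. It does not cover the confident case. An investigator sure that rituximab was responsible has no doubt to declare and correctly enters Not Related under 12.3.

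A second reply is that tazemetostat is the named investigational product, so judging causality against it alone is a deliberate convention. Sections 9.2.5 and 12.2.5 fit that reading. Section 10.1 and the wording of 14.7, 12.3.2 and the synopsis do not.

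A reader might also infer more than the documents support:

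- That rituximab toxicity escapes the safety objective or all the stopping boundaries. The objective and the two grade >3 boundaries count events whatever their cause.
- That an event attributed to both drugs cannot be coded. It can be coded Related.
- That every AE in Cycles 1 to 6 is affected. Only events attributed solely to rituximab are.
- That sites will shift rituximab reactions onto tazemetostat and so trigger Table 1. No passage leads them to do so, and 7.4.2 treats rituximab toxicity separately.
- That the case report form has no rituximab causality item. The form is not among the documents, so this cannot be checked.

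**Conclusion.** The point holds as a mismatch of definitions. Section 12.3 is the only causality assessment the protocol describes. It covers one of two drugs, while the fatality rule, follow-up to resolution and the synopsis table refer to treatment as a whole. If 12.3 supplies the answer for those uses, rituximab-only events are missing from the first two of these: the relatedness breakdown and the required follow-up. A death confidently attributed to rituximab could also be overlooked when the fatality rule is applied.

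The conclusion assumes that 12.3 is followed as written, that the case report form mirrors it, and that no other source of attribution is consulted. The probabilities in the working rest on assumed rates.

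For a trial run to its planned size, this deserves correction before enrolment. For this trial the remaining effect is small: 5 subjects were treated, and the SAP, which supersedes the protocol's statistical section, plans AE listings without any restriction to related events. The stopping-boundary table in Appendix 5 is not in the text available and was not checked.

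**What to change.** 1. Define study drug and study treatment once in the protocol and use each term only in that sense.
2. In 12.3 and on the AE/SAE form, record causality separately for tazemetostat and for rituximab, and allow both to be marked.
3. Reconcile 12.3, 12.3.2, 14.7 and the synopsis so that each states which attribution it uses. Which attribution should govern a halt or a dose change is for the sponsor to settle and is not proposed here.

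The cost is one further item per AE if the form does not already hold it, a few lines of text, slightly more data entry, and possibly more events reported as treatment-related. With the trial closed, it would be enough for the synoptic report to say that relationship was assessed against tazemetostat only, if that is confirmed from the form.
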